#### 8.1.6. Exploratory Endpoints

# 8.2. Safety Assessments

Planned timepoints for all safety assessments are provided in the SoA.

#### 8.2.1. Physical Examinations

- A physical examination will include, at a minimum, assessments of the cardiovascular, respiratory, gastrointestinal and neurological systems.
- Investigators should pay special attention to clinical signs related to previous serious illnesses.

#### 8.2.2. Vital Signs

- BP and pulse measurements will be assessed in a resting position with a completely automated device. Manual techniques will be used only if an automated device is not available.
- BP and pulse measurements should be preceded by at least 5 minutes of rest for the participant in a quiet setting without distractions (eg, television, cell phones).
- Vital signs will be measured after 5 minutes of rest and will include temperature, systolic and diastolic BP, pulse, and respiratory rate. Three readings of BP and pulse will be taken. The first reading should be rejected. The second and third readings should be averaged to give the measurement to be recorded in the eCRF.

### 8.2.3. Electrocardiograms

- Sites or designee shall transmit all study-required ECGs obtained to the ECG vendor. If multiple ECGs have been obtained for the same participant on the same date, the first readable ECG shall be entered as the visit ECG, and all others shall be entered as unscheduled. All readable ECGs received by the vendor shall be sent for ECG vendor, cardiologist over-read. The sponsor will receive all ECG data, including vendor cardiologist assessments, in the data transfer, including those ECGs that could not be evaluated.
- On Visit 2, Day 1, two 12-lead ECGs will be performed; 1 before surgery and 1 after surgery.
- A 12-lead ECG will be obtained in the supine or semi-recumbent position as outlined in the SoA (see Section 1.3) using an ECG machine that automatically calculates the heart rate and measures PR, QRS, QT, and QTc intervals.
- The X-axis speed will be a standard 25 mm per second; the ECG tracing will be kept at the study site. Measurements will be recorded for the following parameters in lead II or lead III: heart rate, PR interval, QRS duration, QT interval, and QTc. All ECGs will be clinically interpreted by the investigator or sub-investigator.

AGN-151607

# 8.2.4. Clinical Safety Laboratory Assessments

- See Appendix 2, Section 10.2, for the list of clinical laboratory tests to be performed and the SoA for the timing and frequency.
  - The investigator must review the laboratory report, document this review, and record any clinically relevant changes occurring during the study in the AE section of the eCRF. The laboratory reports must be filed with the source documents. Clinically significant abnormal laboratory findings are those which are not associated with the underlying disease, unless judged by the investigator to be more severe than expected for the participant's condition.
- All laboratory tests with values considered clinically significant during participation in the study should be repeated until the values return to normal or baseline or are no longer considered clinically significant by the investigator.
  - If such values do not return to normal/baseline within a period of time judged reasonable by the investigator, the etiology should be identified and the sponsor notified.
  - All protocol-required laboratory assessments, as defined in Appendix 2, Section 10.2, must be conducted in accordance with the laboratory manual and the SoA.
  - If laboratory values from non-protocol specified laboratory assessments performed at the institution's local laboratory require a change in participant management or are considered clinically significant by the investigator (eg, SAE or AE or dose modification), then the results must be recorded in the eCRF.

# 8.2.5. Pulmonary Function Testing

Study participant pulmonary function will be assessed at the screening visit and Day 30 using forced procedures and compared across all 3 study groups (refer to study reference guide). Note, if local policies contraindicate or prohibit PFT assessments due to potential for viral spread or microbial precautions, then the PFT is not required after explicit approval from the sponsor. If PFT assessments are not prohibited by local regulations/policies, then the PFTs should be conducted.

Spirometry testing will be conducted by a pulmonologist, pulmonary technician, respiratory therapist, nurse, and/or other appropriate personnel trained in this procedure, following the American Thoracic Society (ATS) Standardization of Spirometry guidelines (Miller, 2005). To demonstrate reproducibility of results, participants will be required to perform at least 3 acceptable spirometry maneuvers up to a maximum of 8 attempts. The results of all respiratory measures will be reviewed for clinically significant findings.

The assessments will include the following:

- 1. Forced vital capacity (FVC) measured from a maximal forced exhalation
- 2. Forced expiratory volume (FEV) in 1 second (FEV1), 3 seconds (FEV3) and 6 seconds (FEV6)

# 8.2.6. Suicidal Risk Monitoring

Not applicable.

AGN-151607

#### 8.2.7. Immunogenicity Assessments

Blood samples will be collected from all participants prior to dosing on Day 1 and at the Day 30 and Day 90 follow-up visits. A 2-tier assay approach will be used for the detection of binding and neutralizing antibodies to AGN-151607 in human serum. In tier 1, serum samples will be screened using a validated enzyme-linked immunosorbent assay (ELISA). The positive samples will subsequently be immune depleted to confirm that the antibodies were specifically binding to AGN-151607 and then titered to assess the magnitude of antibodies present. In tier 2, only samples that are considered positive in the ELISA will be tested for neutralizing antibodies to AGN-151607 using a validated assay.

Samples may be stored for a maximum of 2 years (or according to local regulations) following the last participant's last visit for the study at a facility selected by the sponsor to enable further analysis of immune responses to AGN-151607.

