#### CONFIDENTIAL

#### AGN-151607

Study Period	Screening a				D	ays 1 to	60					Day 61	through l	Day 360		
Visit Number	V1	V2	V3	V4 b	V5 b	V6 b	V7 b	TC1	V8	V9	V10	V11	V12	V13	TC2	Early
Day Number	(up to 28 days)	D1	D2	D3	D4	D5	D6	D14	D30	D60	D90	D180	D270	D360	D367 d	Disc e
Visit Windows	-	-	-	-	-	-	-	$\pm 3d$	$\pm 3d$	$\pm 3d$	$\pm 7d$	$\pm 7d$	$\pm 7d$	$\pm 7d$	V13 + 7d (+ 7d)	-
AFEQT	Х								Х		Х	Х				Xs
AFSS	Х								Х		Х	Х				Xs
DASI	Х								Х		Х	Х				Xs
EuroSCORE IIt	Х															
SF-12v2	Х								Х		Х	Х				Xs
EQ-5D-5L	Х								Х		Х	Х				Xs
Record discharge from ICU		Х	Х	Х	Х	Х	Х									
Record discharge from hospital			Х	Х	Х	Х	Х									
Record any additional healthcare resource utilization								Х	Х	Х	Х	Х	Х	Х	X	Х
Serum sampling for immunogenicity assessment u	X								Х		Х					

AE = adverse event; AF = atrial fibrillation; AFEQT = Atrial Fibrillation Effect on Quality-of-life Questionnaire; AFSS = University of Toronto Atrial Fibrillation Severity Scale; D(d) = day; DASI = Duke Activity Status Index; Disc = discontinuation; ECG = electrocardiogram; EQ-5D-5L = A measure of health-related quality of life developed by the EuroQol Group; FU = follow-up; ICU = intensive care unit; PFT = pulmonary function test; SAE = serious adverse event; SF-12v2 = Short Form-12 Health Survey, version 2; TC = telephone call; V = visit

a Screening and randomization activities can occur on the same day. If screening and randomization occur on the same day, all assessments for Visit 1 and Visit 2 should be completed. Duplicate assessments (eg, laboratory assessments) do not have to be completed twice; please note a 12-lead ECG is required both before and after surgery.

b These visits are optional and are only required if the participant is still hospitalized. Participants may remain in the hospital beyond Day 6, based on the recovery from surgery. The study visit procedures will have to be performed each day until discharge.

c In case of early discontinuation, attempts will be made to follow-up with the participant.

d Day 367 must be at least 7 days and should be no more than 14 days after Visit 13 (Day 360).

e On Day 1, assessments to be performed prior to surgery.

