4.0 Introduction

This statistical analysis plan (SAP) provides a detailed elaboration of the statistical analyses of the efficacy and safety data as specified in the final protocol of Study 1925-201-008 (amendment 1 version dated 25 September 2020). Specifications of tables, figures, and data listings are contained in a separate document.

This is a phase 2, multi-center, randomized, double-blind, placebo-controlled, dose-ranging study in patients 55-90 years of age who are scheduled to undergo open-chest cardiac surgery.

The length of this study will be 367 days, not including the screening visit, which may occur up to 28 days before the first study day (randomization). Signed informed consent from the participant will be obtained before any study-related procedures are begun. Patients meeting the inclusion/exclusion criteria will be randomized (1:1:1 ratio) to one of three treatment arms at the end of the screening period. Primary and secondary efficacy assessments will be assessed for 30 days post-surgery. Additional efficacy and exploratory assessments will be assessed through Day 367 post-surgery. All participants will be followed through Day 367 for safety assessments. Every attempt will be made for participants who prematurely discontinue from the study, regardless of cause, to be seen for a final evaluation.

The study schema is presented below.

D = study day; TC = telephone call; U = units; V = Visit

a Hospital discharge could take more than 6 days.

The schedule of evaluations is presented in the Table 4–1 below.

Page 7

Table 4–1Schedule of Evaluations: Study 1925-201-008

Study Period	Screening ^a	Days 1 to 60						Day 61 through Day 360								
Visit Number	V1	V2	V3	V4 ^b	V5 ^b	V6 ^b	V7 ^b	TC1	V8	V9	V10	V11	V12	V13	TC2	Early
Day Number	(up to 28 days)	D1	D2	D3	D4	D5	D6	D14	D30	D60	D90	D180	D270	D360	D367 ^d	Disc
Visit Windows	-	-	-	-	-	-	-	± 3d	± 3d	± 3d	± 7d	± 7d	± 7d	± 7d	V13 + 7d (+ 7d)	-
Informed consent	Х															
Inclusion and exclusion criteria	Xe	Х														
Demography	Х															
Physical examination	Х								Х					Xf		Х
Medical history	X															
Urine pregnancy test (for women of childbearing potential) ^{e,g}	Х	x														
Laboratory assessments ^{e,h}	Х	Х					Х		Х	Xi	Xi			Xi		Х
Sample collection for biomarker assessment ^e		Х	х	Х	Х											
12-lead ECG ^j	Х	Х	Х	Х	Х	Х	Х		Х	Xk	Xk	Xk	Xk	Xk		Х
ECG patch		Х	Х	Х	Х	Х	Х	Х	X ¹	X ^m	Х					
Vital signs ^{e,n}	Х	Х	Х	Х	Х	Х	Х		Х	Х	Х	Х	Х	Х		Х

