11.5 Other Safety Parameters

11.5.1 Immunogenicity Assessments

Blood samples will be collected from all participants prior to dosing on day 1 and at the day 30 and day 90 follow-up visits. A 2-tier assay approach will be used for the detection of binding and neutralizing antibodies to AGN-151607 in human serum.

Immunogenicity findings (positive) will be tabulated with the number and percentage of participants at each visit separately for each AGN-151607 treatment group. Percentages will be based on the number of treated participants with interpretable antibody assays in each treatment group at the specified visit. A cumulative summary based on positive findings at any visit will be done for each AGN-151607 treatment group.

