15.0 Data Handling Conventions

15.1 Visit Time Windows

Table 15–1 presents the visits assigned for safety analyses and the corresponding range of treatment days (window) during which an actual visit may occur. Unless otherwise specified, efficacy parameters collected by visit (e.g., Quality of Life Outcomes) will use the same windows during which an actual visit may occur. All analyzable ePatch data collected from ePatches with a start date within the visit window will be included in the analysis for the derived visit for Days 60, 90, 180, 270, and 360.

Scheduled Visit	Study Day ^a	Time Window (Study Day Range)
Baseline	1	1
Day 2	2	2
Day 3	3	3
Day 4	4	4
Day 5	5	5
Day 6	6	[6, 10]
Day 14	14	[11, 21]
Day 30	30	[22, 45]
Day 60	60	[46, 75]
Day 90	90	[76, 135]
Day 180	180	[136, 225]
Day 270	270	[226, 315]
Day 360	360	> 315 days

Table 15–1Analysis Visit Windows

a Relative to the date of the study treatment. Day 1 = the date of the study treatment.

If the assessment date (if the assessment date is unavailable, use visit date instead) is on or after the date of the study treatment, the study day is calculated by assessment date – date of the study treatment + 1. If the assessment date is before the date of the study treatment, the study day is calculated by assessment date – date of the study treatment. Therefore, a negative day indicates a day before the start of the study treatment.

If a subject has 2 or more visits within the same window, the last visit with a non-missing value will be used for analysis. All postbaseline assessments will be considered for PCS categorization. All assessments will be included in respective listings.

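### The pre-dose antibody sample is placed on Day 1 in the text but at Screening in both schedules, no rule names the antibody baseline, and the planned summary does not separate existing from treatment-induced antibody

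*Protocol*

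**What the plan says.** **Timing in the text.** Protocol 8.2.7 states: "Blood samples will be collected from all participants prior to dosing on Day 1 and at the Day 30 and Day 90 follow-up visits". SAP 11.5.1 repeats this: "Blood samples will be collected from all participants prior to dosing on day 1 and at the day 30 and day 90 follow-up visits".

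**Timing in the schedules.** In Protocol Section 1.3 the row "Serum sampling for immunogenicity assessment" is marked at Screening (Visit 1), Day 30 (Visit 8) and Day 90 (Visit 10). It has no mark at Visit 2, which is Day 1. SAP Table 4–1 shows the same pattern. Screening may precede Day 1 by up to 28 days (SAP 4.0), although footnote a to both schedules allows the two to coincide: "Screening and randomization activities can occur on the same day".

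**Baseline rules.** Three places in the SAP bear on this:
- Table 15–1 (SAP 15.1) gives Baseline the single study day 1. It has no row for earlier days, and "a negative day indicates a day before the start of the study treatment".
- SAP 11.0 takes the last non-missing value before treatment as baseline, but names only physical examination, laboratory tests, vital signs and ECG.
- SAP 15.2 has a similar rule for safety parameters, worded for participants with repeated assessments before treatment.

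**Analysis.** SAP 11.5.1 says: "Immunogenicity findings (positive) will be tabulated with the number and percentage of participants at each visit". This is done separately for each AGN-151607 group, with a cumulative summary of positives at any visit. It defines no seroconversion, no change from baseline and no split by pre-dose status.

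**The concern.** A pre-dose antibody sample shows who already had antibody, so that a positive at Day 30 or Day 90 can be attributed to the injection or not. Here the sample's timing is contradictory, its role as baseline is not expressly assigned, and the planned tables do not use it for that purpose.

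The last gap matters most. Only the AGN-151607 arms are tabulated, so no placebo rate is planned against which background positivity could be judged. The participant's own pre-dose result is then the only planned information that could separate existing from induced antibody. Prior exposure is possible under the entry criteria. Exclusion 2.02 bars botulinum toxin use only within 6 months of randomization, and exclusion 2.03 relies on medical history, not serology, for prior immunization. At stake is whether the immunogenicity summary can be read as an effect of treatment.

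**Working it through.** No sample-size or power arithmetic applies, and the plan gives no figure to reproduce. The check sets the relevant places side by side, applies the SAP's study-day formula, and follows antibody patterns through the planned tables.

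**1. Is the timing mismatch real?** The serum row's marks fall in the same columns as the Screening, Day 30 and Day 90 marks of the questionnaire rows (AFEQT, DASI, EQ-5D-5L). Protocol Table 8-8 confirms that those questionnaires start at Screening. The biomarker row, whose first draw is on Day 1 before surgery, starts one column later. The mark is therefore at Screening, and the mismatch does not come from a broken table.

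**2. Where does a Screening sample fall in Table 15–1?** SAP 15.1 gives:
- before treatment: study day = assessment date − treatment date;
- on or after treatment: study day = assessment date − treatment date + 1.

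| Sample drawn | Study day | Table 15–1 window |
|---|---|---|
| 28 days before treatment | −28 | none |
| 1 day before treatment | −1 | none |
| Same day as treatment | 0 + 1 = 1 | Baseline |

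On Table 15–1 alone, a sample from day −28 to −1 has no visit. A same-day sample has one.

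**3. Does another rule assign it?**
- SAP 11.0: immunogenicity is absent from the baseline rule and from that section's list of safety parameters. Protocol 9.4.2 lists it as a safety parameter but leaves it out of the baseline rule in the same paragraph.
- SAP 15.2: the rule would take any Screening sample as baseline. Its condition is more than one pre-treatment assessment, whereas the schedule plans one antibody sample before dosing. It applies by near analogy, not expressly.
- Protocol 8.8 says that samples under that section will be tested for immunogenicity as well as biomarkers. SAP 10.4.3 assigns the Day 1 to Day 4 samples to biomarkers only. This leaves the matter unsettled.

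**4. What would the planned tables show?** Consider four patterns of positive (+) and negative (−) results:

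| Pre-dose | Day 30 | Day 90 | Meaning | Counted at Day 30 | Counted at any visit |
|---|---|---|---|---|---|
| − | + | + | new after dosing | yes | yes |
| + | + | + | already present | yes | yes |
| + | − | − | present before dosing only | no | yes if the pre-dose sample counts as a visit; otherwise no |
| − | − | − | negative throughout | no | no |

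The first two rows are reported identically. The third depends on whether a pre-dose sample counts as a visit. SAP 11.5.1 does not say. Under a literal reading of Table 15–1, the answer would also turn on whether the sample was drawn on Day 1 or earlier. A Baseline row in the by-visit table would show the overall percentage positive before dosing, but not which participants those were at Day 30 or Day 90.

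**The case against.** The strongest reply is that little is lost in practice, and much of it stands.

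A reader might infer from Table 15–1 that a Screening sample is excluded and baseline serostatus lost. The documents do not support that. The SAP uses Screening values as baseline elsewhere: quality of life is labelled that way in SAP 10.4.2, and SAP 11.5.2 plans changes from baseline for pulmonary function, which is measured only at Screening and Day 30. Table 15–1 is therefore not applied as an exclusive baseline rule. SAP 15.2 offers a sensible rule by analogy, immunogenicity sits under the other safety parameters in SAP 11.5, and SAP 15.1 places every assessment in the listings.

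A reader might also infer that a site cannot follow both instructions. It can: same-day screening satisfies both, and a site could draw at both visits.

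A further objection is that a sample drawn exactly on Day 1 would leave the Day 30 and Day 90 percentages unchanged, since SAP 11.5.1 plans no baseline adjustment. That is correct. The mixing of existing and induced antibody comes from the design of the table, not from the timing mismatch. It is a separate weakness with its own remedy.

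Finally, the exclusions and the immune-depletion confirmation of ELISA positives in Protocol 8.2.7 may make pre-dose positives uncommon. That may be so, but a small number is no reason to leave their handling undefined.

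**Conclusion.** The concern holds in three limited parts. The text and the schedules disagree on the visit for the pre-dose antibody sample in both documents. No SAP rule expressly assigns the antibody baseline, although an analyst could reasonably settle on the last pre-treatment sample. The planned summary of positives cannot distinguish existing from treatment-induced antibody, and it does not say whether pre-dose positives enter the cumulative count.

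The number of participants affected cannot be derived. The documents give neither a pre-dose positivity rate nor the share of participants who would be screened before Day 1, so a count per arm would rest entirely on assumption. The conclusion about the tables needs neither figure; it follows from the wording of SAP 11.5.1.

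This is a minor point about a descriptive safety summary. It does not affect the primary endpoint, the significance level or power.

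**What to change.** 1. Reconcile the serum row in Protocol Section 1.3 and SAP Table 4–1 with Protocol 8.2.7 and SAP 11.5.1, so that all four name the same pre-dose visit.
2. State in SAP 11.5.1 that the antibody baseline is the last sample drawn before injection, whatever its visit label or study day. This works whichever visit is kept.
3. Tabulate Day 30, Day 90 and cumulative post-baseline positives by that baseline status (negative, positive, missing).
4. State that a positive result before dosing does not count in the cumulative post-dose summary.

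The cost is one corrected row or sentence in the protocol, the matching row and a few sentences in the SAP, and a small change to one table layout. No additional sample, visit or assay is needed.

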# 8.3. Adverse Events and Serious Adverse Events

The definitions of an AE or SAE can be found in Appendix 3, Section 10.3.

AEs will be reported by the participant or, when appropriate, by a caregiver.

The investigator and any qualified designees are responsible for detecting, documenting, and recording events that meet the definition of an AE or SAE and remain responsible for following up AEs that are serious, considered related to the study intervention or study procedures, or that caused the participant to discontinue the study (see Section 7).

#### 8.3.1. Time Period and Frequency for Collecting Adverse Event and Serious Adverse Event Information

All AEs/SAEs from the signing of the ICF until the Day 367 follow-up visit/early discontinuation visit will be collected at the timepoints specified in the SoA (Section 1.3), and as observed or reported spontaneously by study participants.

Medical occurrences that begin before the start of study intervention, but after obtaining informed consent, will be recorded as an AE.

All SAEs will be recorded and reported to the sponsor or designee within 24 hours, as indicated in Appendix 3, Section 10.3. The investigator will submit any updated SAE data to the sponsor within 24 hours of it being available.

Investigators are not obligated to actively seek AE or SAE information after conclusion of the study participation. However, if the investigator learns of any SAE, including a death, at any time after a participant has been discharged from the study, and he/she considers the event to be reasonably related to the study intervention or study participation, the investigator must promptly notify the sponsor.

The method of recording, evaluating, and assessing causality of AEs and SAEs and the procedures for completing and transmitting SAE reports are provided in Appendix 3, Section 10.3. Assessment of causality to both the study intervention and the study procedures are required for reporting each SAE. For the purpose of causality assessment, "study procedure" on the SAE reporting form means the procedure of injecting the study intervention into the

